10.12 Appendix 12: Grading and Management of Cytokine Release Syndrome

Harmonized definitions and grading criteria for CRS, per the American Society for Transplantation and Cellular Therapy (ASTCT), formerly American Society for Blood and Marrow Transplantation, (ASBMT), are presented below.

Genmab

Grading of Cytokine Release Syndrome

CRS parameter	Grade 1	Grade 2	Grade 3	Grade 4	Grade 5	
Fever ^a	≥38.0°C	≥38.0°C	≥38.0°C	≥38.0°C		
With hypotension ^b	None	Not requiring vasopressors	Requiring 1 vasopressor with or without vasopressin	Requiring ≥ 2 vasopressors (excluding vasopressin)	Death due to CRS in which another cause is not the	
And/or hypoxia ^b	None	Requiring low- flow (≤6 L/minute) nasal cannula or blow-by	Requiring high-flow (>6 L/minute) nasal cannula, facemask, nonrebreather mask, or venturi mask	Requiring positive pressure ventilation ^c (eg, CPAP, BiPAP, intubation and mechanical ventilation)		

BiPAP=bilevel positive airway pressure; CPAP=continuous positive airway pressure; CRS=cytokine release syndrome; CTCAE= Common Terminology Criteria for Adverse Events.

Note: organ toxicities or constitutional symptoms associated with CRS may be graded according to CTCAE but they do not influence CRS grading.

- Fever is defined as temperature ≥38.0°C not attributable to any other cause, with or without constitutional symptoms (eg, myalgia, arthralgia, malaise). In subjects who have CRS receiving antipyretics, anticytokine therapy, and/or corticosteroids, fever is no longer required to grade subsequent CRS severity. In this case, CRS grading is driven by hypotension and/or hypoxia.
- CRS grade is determined by the more severe event: hypotension or hypoxia not attributable to any other cause. For example, a subject with temperature of 39.5°C, hypotension requiring 1 vasopressor, and hypoxia requiring low-flow nasal cannula is classified as grade 3 CRS. Both systolic blood pressure and mean arterial pressure are acceptable for blood pressure measurement. No specific limits are required, but hypotension should be determined on a case-bycase basis, accounting for age and the subject's individual baseline, ie, a blood pressure that is below the normal expected for an individual in a given environment.
- Intubation of a subject without hypoxia for the possible neurologic compromise of a patent airway alone or for a procedure is not by definition grade 4 CRS.

Source: (Lee et al., 2019)

Confidential Page 132 of 162

Document Number: TMF-380962

Version: 3.0

10.13 Appendix 13: CRS Management Guidance Based on the American Society for Transplantation and Cellular Therapy (ASTCT)^a Guidelines

Genmab

Tra	Transplantation and Cellular Therapy (ASTCT) ^a Guidelines				
CRS Grade ^a	Supportive Care	Anticytokine Therapy ^b	Glucocorticoids		
Grade 1	Hold GEN3017 until resolution of CRS. In-person evaluation by medical professional, ideally at site or center with experience managing CRS. Investigate for infection and rapidly startup broad-spectrum antibiotics. Continuation of antibiotic therapy is recommended until fever and any existing neutropenia resolve. Supportive care per institutional standard of care (antipyretics and IV hydration) Closely monitor neurologic status	Consider anticytokine therapye in certain cases, eg, advanced age, high tumor burden, circulating tumor cells, fever refractory to antipyretics. Note: In case of concurrent ICANS choose alternative to tocilizumab (eg, siltuximab, anakinra)	Dexamethasone 10-20 mg per day (or equivalent) may be initiated. Note: In case of concurrent ICANS, initiation of corticosteroids are highly recommended (see ICANS guidelines in Section 10.12).		
Grade 2	Hold GEN3017 until resolution of CRS. In-person evaluation by medical professional, ideally at site or center with experience managing CRS. Investigate for infection and rapidly startup broad-spectrum antibiotics. Continuation of antibiotic therapy is recommended until fever and any existing neutropenia resolve. Continuous cardiac telemetry and pulse oximetry as indicated IV fluids bolus for hypotension with 0.5 to 1.0 L isotonic fluids Supplemental oxygen as indicated	Anticytokine therapy recommended. ^e If CRS is refractory to initial cytokine therapy, initiate/increase dose of corticosteroid therapy and consider alternative anticytokine therapy. Note: In case of concurrent ICANS choose alternative to tocilizumab (eg, siltuximab, anakinra)	Consider dexamethasone 10-20 mg per day (or equivalent). Note: In case of concurrent ICANS, initiation of corticosteroids is highly recommended (see ICANS guidelines in Section 10.12).		
Grade 3	Hold GEN3017 until resolution of CRS. In-person evaluation by medical professional, ideally at site or center with experience managing CRS. Investigate for infection and rapidly startup broad-spectrum	Anticytokine therapy recommended. ^c If CRS is refractory to initial cytokine therapy, initiate/increase dose of corticosteroid therapy and consider alternative anticytokine therapy.	Dexamethasone (eg, 10-20 mg IV every 6 hours). If no response, initiate methylprednisolone 1000 mg/day.		

Confidential Page 133 of 162

Genmab

Document Number: TMF-380962

Version: 3.0

CRS	Supportive Care	Anticytokine Therapy ^b	Glucocorticoids
Gradea			Giacocoi acoius
	antibiotics. Continuation of antibiotic therapy is recommended until fever and any existing neutropenia resolve.	Note: In case of concurrent ICANS choose alternative to tocilizumab (eg, siltuximab, anakinra)	
	Management in intensive care unit.		
	Vasopressor support and/or supplemental oxygen.		
	Consider cardiac echocardiogram.		
	IV fluids as indicated.		
Grade 4	Permanently discontinue GEN3017.	Anticytokine therapy recommended. ^c	Dexamethasone (eg, 10-20 mg IV every 6 hours). If no response,
	In-person evaluation by medical professional, ideally at site or center with experience managing CRS.	If CRS is refractory to initial cytokine therapy, initiate/increase dose of corticosteroid therapy and consider alternative	initiate methylprednisolone 1000 mg/day.
	Investigate for infection and rapidly startup broad-spectrum antibiotics. Continuation of	anticytokine therapy. Note: In case of concurrent	
	antibiotic therapy is recommended until fever and any existing neutropenia resolve.	ICANS choose alternative to tocilizumab (eg, siltuximab, anakinra)	
	Management in intensive care unit.		
	Mechanical ventilation and/or renal replacement therapy may be required		
	Vasopressor support as indicated		
	IV fluids as indicated.		
	Consider and assess for development of macrophage activation syndrome/ hemophagocytic lymphohistiocytosis (MAS/HLH) ^d , including monitoring of fibrinogen and		
	triglyceride levels		
MAS/HLH	If MAS/HLH is combined with CRS, permanently discontinue GEN3017.	First-line treatment: Includes II tocilizumab, unless tocilizumab for the management of CRS. Glindicated for the initial treatment	was already administered lucocorticoids are also
	Intensive supportive care is essential because of frequent life-	of the cause (CRS Grade 4 treatment recommendations	

Confidential Page 134 of 162

Document Number: TMF-380962

Version: 3.0

CRS Grade ^a	Supportive Care	Anticytokine Therapy ^b	Glucocorticoids
	threatening, severe manifestations at presentation. Appropriate broad-spectrum	event that severe CRS is not responding to tocilizumab a corticosteroids. Anakinra should be given until resolutio CRS with a daily dose of 100 mg SC. gal In more severe MAS/HLH cases, especially if combined with CRS and/or neurotoxicity, anakinra 100-200 mg SC twice daily (every 12 hours), or higher doses (up to 8	
	antiviral, antibacterial, antifungal prophylaxis, and treatment must be initiated. The elimination of triggers (particularly infection) is crucial to remove the stimuli that initiate the abnormal immune system activation.		
		In case of rapidly progressing c CRS, anakinra should be admin treatment.	

CRS=cytokine release syndrome; ICANS=immune effector cell-associated neurotoxicity syndrome; IV=intravenous(ly); MAS/HLH=macrophage activation syndrome/hemophagocytic lymphohistiocytosis; SC=subcutaneous(ly).

- a. Source: (Lee et al., 2019)
- b. Refer to tocilizumab, siltuximab, or anakinra local prescribing information for product details.
- c. High-dose vasopressors in table below.
- d. Anakinra should be considered in the event that severe CRS is not responding to tocilizumab and corticosteroid.
- e. Suggested anticytokine dosing:
 - Tocilizumab 8 mg/kg IV over 1 hour (not to exceed 800 mg per dose). Repeat tocilizumab after at least 8 hours as needed. Maximum of 2 doses in a 24-hour period.
 - Siltuximab 11 mg/kg IV over 1 hour, 1 time only.
 - Anakinra 100 mg SC once/day.
 - In more severe CRS cases, especially if combined with MAS/HLH and/or neurotoxicity, anakinra 100-200 mg twice daily (every 12 hours) SC should be given until resolution of CRS and other concurrent T-cell toxicities, like neurotoxicity and/or MAS/HLH which could benefit from anakinra treatment.

Confidential Page 135 of 162

Document Number: TMF-380962

Version: 3.0

High-Dose Vasopressors (all Doses are Required for ≥3 Hours)

Pressor	Dose
Norepinephrine monotherapy	≥20 μg/min
Dopamine monotherapy	≥10 µg/kg/min
Phenylephrine monotherapy	≥200 µg/min
Epinephrine monotherapy	≥10 µg/min
If on vasopressin	Vasopressin 1 norepinephrine equivalent of ≥10 µg/min ^a
If on combination vasopressors (not vasopressin)	Norepinephrine equivalent of ≥20 µg/min ^a

a. Vasopressor equivalent equation: norepinephrine equivalent dose = [norepinephrine (μg/min)] + [dopamine (μg/kg/min) /

Confidential Page 136 of 162

^{2] + [}epinephrine (µg/min)] + [phenylephrine (µg/min) / 10] Source: (Lee et al., 2014)

Version: 3.0

10.14 Appendix 14: ASTCT ICANS Consensus Grading and Management

Management Guidelines for Immune Effector Cell-Associated Neurotoxicity Syndrome (ICANS) Based on ASTCT Guidelines

Genmab

Hold GEN3017 until resolution of ICANS.	No concurrent CRS:	
 Supportive care per institutional standard of care Closely monitor neurologic status Recommend initiating prophylactic non-sedating anti-seizure medication until resolution of ICANS Aspiration precautions Recommend brain imaging and EEG per institutional guidelines 	Anticytokine therapy not indicated Concurrent CRS: Anticytokine therapy indicated: Choose alternative to tocilizumab (eg, siltuximab, anakinra) if possible. (Refer to CRS Management Guidance Based on the American Society for Transplantation and Cellular Therapy (ASTCT) Guidelines table in Section 10.13.) Consider anakinra as a daily dose of 100 mg SC or 200 mg SC (100 mg every 12 hours) depending on the severity of neurotoxicity and other concurrent toxicities. Anakinra should be given until resolution of neurotoxicity and other concurrent toxicities which could benefit from anakinra treatment. Consider siltuximab, 11 mg/kg IV over	Dexamethasone, 10 mg IV every 12 hours
 Hold GEN3017 until resolution of ICANS. Supportive care per institutional standard of 	No concurrent CRS: Anticytokine therapy not indicated.	Dexamethasone at 10- 20 mg IV every 12 hours
 Closely monitor neurologic status Recommend initiating prophylactic non-sedating anti-seizure medication until resolution of ICANS (eg, levetiracetam) 	Anticytokine therapy indicated: Choose alternative to tocilizumab (eg, siltuximab, anakinra) if possible. (Refer to CRS Management Guidance	
	 Recommend initiating prophylactic non-sedating anti-seizure medication until resolution of ICANS Aspiration precautions Recommend brain imaging and EEG per institutional guidelines Supportive care per institutional standard of care Closely monitor neurologic status Recommend initiating prophylactic non-sedating anti-seizure medication until resolution of ICANS 	 neurologic status Recommend initiating prophylactic non-sedating anti-seizure medication until resolution of ICANS Aspiration precautions Recommend brain imaging and EEG per institutional guidelines Consider anakinra as a daily dose of 100 mg SC or 200 mg SC (100 mg every 12 hours) depending on the severity of neurotoxicity and other concurrent toxicities. Anakinra should be given until resolution of ICANS. Hold GEN3017 until resolution of ICANS. Supportive care per institutional standard of care Closely monitor neurologic status Recommend initiating prophylactic non-sedating anti-seizure medication until resolution of ICANS (eg, levetiracetam) indicated: Choose alternative to tocilizumab (eg, siltuximab, anakinra) if possible. (Refer to CRS Management Guidance Consider anakinra as a daily dose of 100 mg SC or 200 mg SC (100 mg every 12 hours) depending on the severity of neurotoxicity and other concurrent toxicities. Anakinra should be given until resolution of neurotoxicity and other concurrent toxicities which could benefit from anakinra treatment. Consider siltuximab, anakinra) if possible. (Refer to CRS Anticytokine therapy indicated: Choose alternative to tocilizumab (eg, siltuximab, anakinra) if possible. (Refer to CRS Management Guidance

Confidential Page 137 of 162

Genmab

Document Number: TMF-380962

Version: 3.0

Neurologic Toxicities	Supportive Care	Anticytokine Therapy	Corticosteroids
Encephalopathy: limiting instrumental ADLs Dysphasia: moderate impairing ability to communicate spontaneously	 Continuous cardiac telemetry and pulse oximetry as indicated Closely monitor neurologic status with serial neurologic examinations to include fundoscopy. Consider neurology consult. Perform brain imaging (eg, MRI), EEG, and lumbar puncture (with opening pressure) if no contraindications Prophylactic non-sedating anti-seizure medication 	(ASTCT) Guidelines table in Section 10.13.) Consider anakinra at a daily dose of 100 mg SC or 200 mg SC (100 mg every 12 hours) depending on the severity of neurotoxicity and other concurrent toxicities. Anakinra should be given until resolution of neurotoxicity and other concurrent toxicities which could benefit from anakinra treatment. Consider siltuximab, 11 mg/kg IV over 1 hour, one time only.	
Grade 3 ICE score ^a 0-2 and/or depressed level of consciousness ^b but awakens to tactile stimulus And clinical seizure focal or generalized that resolves rapidly, or nonconvulsive seizures on EEG that resolve with intervention No motor weakness Focal/local edema on neuroimaging Somnolence-obtundation or stupor Confusion: severe disorientation Encephalopathy: limiting self-care ADLs Dysphasia: severe receptive or expressive characteristics, impairing ability to read, write, or	 Hold GEN3017 until resolution of ICANS. Management in monitored care or intensive care unit. Supportive care per institutional standard of care Closely monitor neurologic status Recommend initiating prophylactic nonsedating anti-seizure medication until resolution of ICANS (eg, levetiracetam) Aspiration precautions Continuous cardiac telemetry and pulse oximetry as indicated Closely monitor neurologic status with serial neurologic status with serial neurologic examinations to include fundoscopy. Consider neurology consult. Perform brain imaging (eg, MRI), EEG, and lumbar puncture (with opening pressure) if no contraindications 	No concurrent CRS: Anticytokine therapy not indicated. Concurrent CRS: Anticytokine therapy indicated: Choose alternative to tocilizumab (eg, siltuximab, anakinra) if possible. (Refer to CRS Management Guidance Based on the American Society for Transplantation and Cellular Therapy (ASTCT) Guidelines table in Section 10.13.) Consider anakinra at a daily dose of 100 mg SC or 200 mg SC (100 mg every 12 hours) depending on the severity of neurotoxicity and other concurrent toxicities. Anakinra should be given until resolution of	Dexamethasone 10-20 mg IV every 6 hours. If no response, initiate methylprednisolone 1000 mg/day.

Confidential Page 138 of 162

Version: 3.0

Neurologic Toxicities	Supportive Care	Anticytokine Therapy	Corticosteroids
	medication • Levetiracetam/non- sedating antiepileptics if subject has seizures	benefit from anakinra treatment. • Consider siltuximab, 11 mg/kg IV over 1 hour, one time only.	
 Grade 4 ICE score^a 0 and patient is unarousable or requires vigorous or repetitive tactile stimuli to arouse or stupor or coma Life-threatening prolonged seizure (>5 min); or repetitive clinical or electrical seizures without return to baseline in between Deep focal motor weakness^c such as hemiparesis or paraparesis Diffuse cerebral edema on neuroimaging^d; decerebrate or decorticate posturing; or cranial nerve VI palsy; or papilledema; or Cushing's triad Life-threatening consequences Urgent intervention indicated Requirement for mechanical ventilation 	 Permanently discontinue GEN3017. Management in monitored care or intensive care unit. Supportive care per institutional standard of care Closely monitor neurologic status Recommend initiating prophylactic nonsedating anti-seizure medication until resolution of ICANS (eg, levetiracetam) Aspiration precautions Continuous cardiac telemetry and pulse oximetry as indicated Closely monitor neurologic status with serial neurologic examinations to include fundoscopy. Consider neurology consult. Perform brain imaging (eg, MRI), EEG, and lumbar puncture (with opening pressure) if no contraindications Prophylactic nonsedating anti-seizure medication Levetiracetam/nonsedating anti-seizures Mechanical ventilation may be required Consider imaging of spine for focal motor weakness Lower intracranial pressure (ICP) by hyperventilation, hyperosmolar therapy with mannitol/hypertonic saline, and/or neurosurgery consultation for 	No concurrent CRS: Anticytokine therapy not indicated. Concurrent CRS: Anticytokine therapy indicated: Choose alternative to tocilizumab (eg, siltuximab, anakinra) if possible. (Refer to CRS Management Guidance Based on the American Society for Transplantation and Cellular Therapy (ASTCT) Guidelines table in Section 10.13.) Consider anakinra at a daily dose of 100 mg SC or 200 mg SC (100 mg every 12 hours) depending on the severity of neurotoxicity and other concurrent toxicities. Anakinra should be given until resolution of neurotoxicity and other concurrent toxicities which could benefit from anakinra treatment. Consider siltuximab, 11 mg/kg IV over 1 hour, one time only.	Dexamethasone 10-20 mg IV every 6 hours. If no response, initiate methylprednisolone 1000 mg/day

Genmab

Confidential Page 139 of 162

Version: 3.0

Neurologic Toxicities	Supportive Care	Anticytokine Therapy	Corticosteroids	
	ventriculoperitoneal shunt in patients with cerebral edema			
	Aggressive management of ICP with institutional standard of care			
Grade 5 (Fatal)				
Death due to ICANS in				
which another cause is				
not the principal factor				
leading to this outcome.				

ADLs=activities of daily living; ASBMT=American Society for Bone Marrow Transplant; ASTCT=American Society for Transplantation and Cellular Therapy; CRS=cytokine release syndrome; CTCAE=Common Terminology Criteria for Adverse Events; EEG=electroencephalogram; ICANS=immune effector cell-associated neurotoxicity syndrome; ICE=immune effector cell-associated encephalopathy; ICP=intracranial pressure; IV=intravenous; MRI=magnetic resonance imaging; SC=subcutaneous.

Note: ICANS grade is determined by the most severe domain event not attributable to any other cause. For example, a subject with an ICE score of 3 who has a generalized seizure is classified as Grade 3 ICANS.

- a. A subject with an ICE score of 0 may be classified as Grade 3 ICANS if awake with global aphasia, but a subject with an ICE score of 0 may be classified as Grade 4 ICANS if unarousable.
- b. Depressed level of consciousness should be attributable to no other cause (eg, no sedating medication).
- c. Tremors and myoclonus associated with immune effector cell therapies may be graded according to CTCAE v5.0, but they do not influence ICANS grading.
- d. Intracranial hemorrhage with or without associated edema is not considered a neurotoxicity feature and is excluded from ICANS grading. It may be graded according to CTCAE v5.0.

Sources: (Lee et al., 2019)

ICANS Assessment and Grading

Neurotoxicity Domain	Grade 1	Grade 2	Grade 3	Grade 4
ICE score ^a	7-9	3-6	0-2	0 (patient is unarousable and unable to perform ICE)
Depressed level of consciousness ^b	Awakens spontaneously	Awakens to voice	Awakens only to tactile stimulus	Patient is unarousable or requires vigorous or repetitive tactile stimuli to arouse. Stupor or coma
Seizure	N/A	N/A	Any clinical seizure focal or generalized that resolves rapidly or nonconvulsive seizures on EEG that resolve with intervention	Life-threatening prolonged seizure (>5 min); or repetitive clinical or electrical seizures without return to baseline in between
Motor findings ^c	N/A	N/A	N/A	Deep focal motor weakness such as hemiparesis or paraparesis
Elevated ICP/cerebral edema	N/A	N/A	Focal/local edema on neuroimaging ^d	Diffuse cerebral edema on neuroimaging; decerebrate or decorticate posturing; or cranial nerve VI palsy; or papilledema; or Cushing's triad

ICANS grade is determined by the most severe event (ICE score, level of consciousness, seizure, motor findings, raised ICP/cerebral edema) not attributable to any other cause; eg, a patient with an ICE score of 3 who has a generalized seizure is classified as grade 3 ICANS. Grade 5 is considered to be fatal.

Confidential Page 140 of 162

Version: 3.0

CTCAE=Common Terminology Criteria for Adverse Events; EEG=electroencephalogram; ICE=immune effector cell-associated encephalopathy; ICP=intracranial pressure; N/A=not applicable.

- a. A patient with an ICE score of 0 may be classified as grade 3 ICANS if awake with global aphasia, but a patient with an ICE score of 0 may be classified as grade 4 ICANS if unarousable.
- b. Depressed level of consciousness should be attributable to no other cause (eg, no sedating medication).
- c. Tremors and myoclonus associated with immune effector cell therapies may be graded according to CTCAE v 5.0, but they do not influence ICANS grading.
- d. Intracranial hemorrhage with or without associated edema is not considered a neurotoxicity feature and is excluded from ICANS grading. It may be graded according to CTCAE v 5.0.

Source: (Lee et al., 2019)

The Immune Effector Cell-Associated Encephalopathy (ICE) Assessment Tool

Cognitive Domain	Task	Points	ICE Scoring
Orientation	Orientation to year	1	10: No impairment
	Orientation to month	1	7-9: Grade 1 ICANS
	Orientation to city	1	3-6: Grade 2 ICANS
	Orientation to hospital	1	0-2: Grade 3 ICANS
Naming	Naming 3 common objects (eg, point to clock, pen, button)	3	0 due to subject unarousable and unable to perform ICE assessment: Grade 4 ICANS
Following commands	Ability to follow simple commands, eg, "Show me two fingers" or "Close your eyes and stick out your tongue"	1	
Writing	Ability to write a standard sentence, eg, "Our national bird is the bald eagle"	1	
Attention	Ability to count backwards from 100 by 10	1	
Maximum ICE Sco	re	10	

ICANS= immune effector cell-associated neurotoxicity syndrome; ICE= immune effector cell-associated encephalopathy. Source: (Lee et al., 2019)

Confidential Page 141 of 162

Document Number: TMF-380962

Version: 3.0

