		refractory ^a grade 3 for >72 hours or grade 4	Manage CRS per current practice guidelines (Section 10.13) and provide supportive therapy, which may include intensive care.
	ICANS (see Section 10.14)	Grade 1 and grade 2	Withhold GEN3017 until resolution of ICANS event to ≤ grade 1 for at least 72 hours.
			Provide supportive therapy and manage per current practice guidelines.
		Grade 3	Withhold GEN3017 until resolution of ICANS event to ≤ grade 1 for at least 72 hours.
			Provide supportive therapy, which may include intensive care, consider neurology evaluation, and manage per current practice guidelines.
			Recurrent grade 3 ICANS: Permanently discontinue GEN3017.
		Grade 4	Permanently discontinue GEN3017.
			Provide supportive therapy, which may include intensive care, consider neurology evaluation, and manage per current practice guidelines.
Hematological (see Section 6.7.2.1 for details) ^b	Platelet count decreased/	≥ Grade 3	Withhold GEN3017 until platelet count is ≥50 × 10 ⁹ /L.
	thrombocytopenia		Platelet infusions may be administered per institutional standards.
	Neutropenia and febrile neutropenia	≥ Grade 3	Withhold GEN3017 until neutrophil count is $\geq 0.5 \times 10^9 / L$.
			Use of growth factors is mandated.
	Anemia	≥ Grade 3	Withhold GEN3017 until hemoglobin is ≥8 g/dL (≥80 g/L or ≥4.9 mmol/L).
			Red blood cell infusions should be administered per institutional standards.

Confidential Page 78 of 162

Document Number: TMF-380962

Version: 3.0

	Adverse Event(s)	Toxicity Grade or Condition (CTCAE v5.0 Except ASTCT for CRS/ICANS and Cairo- Bishop for TLS/CTLS)	Adverse Event Management	
	TLS/CTLS	Any grade	Withhold GEN3017 until resolution of TLS/CTLS event.	
	Tumor flare reaction	Grade 3 and 4	Withhold GEN3017 until improvement to ≤ grade 1. Monitor for signs and symptoms of compression or obstruction due to mass effect secondary to tumor flare, and institute appropriate treatment (Section 10.15).	
	All other non- hematologic AEs	Grade 3a; first occurrence	Withhold GEN3017 until improvement to ≤ grade 2 or resolution to baseline.	
		Grade 3a; recurrent	Second episode of the same AE considered related to GEN3017:	
Other non-hematologic			Withhold GEN3017 until improvement to ≤ grade 2 or resolution to baseline.	
			Permanently discontinue GEN3017 if no improvement within 14 days unless otherwise agreed upon with the sponsor's medical monitor.	
		Grade 4a; first occurrence	Withhold GEN3017.	
			Initiate proper management of the AE.	

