8.3.8 Other Safety Assessments

8.3.8.1 Neurological Evaluation

Assessment for neurotoxicity with a neurologic assessment must be performed during therapy with GEN3017 by trained trial-site staff. An assessment according to ICANS evaluation (Lee et al., 2019) should be performed as indicated in Section 1.3. ICANS assessments must be performed at least daily during CRS events, and once daily during hospitalization if subject was hospitalized. Finally, additional ICANS assessment should always be performed when clinically indicated.

ICANS is a disorder characterized by a pathologic process involving the CNS following any immune therapy that results in the activation or engagement of endogenous or infused immune effector cells, including T cells. ICANS may occur concurrently with CRS or shortly after CRS symptoms subside (but rarely before). Symptoms can be progressive and may include aphasia, altered level of consciousness, delirium, dizziness, encephalopathy, headache, impairment of cognitive skills, motor weakness, tremor, seizures, and cerebral edema (Lee et al., 2019).

The grading of ICANS requires assessment of the 10-point immune effector cell-associated encephalopathy (ICE) score as well as evaluation of 4 other neurologic domains: level of consciousness, seizures, motor symptoms, and signs of raised intracranial pressure/cerebral edema, which may occur with or without encephalopathy. See Section 10.14 for additional details for grading and management of ICANS.

Overall ICANS grade is determined by the most severe event of the neurotoxicity domains (ICE score, level of consciousness, seizure, motor findings, raised intracranial pressure/cerebral edema) not attributable to any other cause. For example: subject with an ICE score of 3 who has a generalized seizure is classified as having grade 3 ICANS.

A subject with an ICE score of 0 may be classified as having grade 3 ICANS if the subject is awake with global aphasia. But a subject with an ICE score of 0 may be classified as having grade 4 ICANS if the subject is unarousable.

A subject with an abnormal ICE score must be assessed to determine if it is due to ICANS or an alternate cause. If not due to ICANS, the relevant condition will be reported as an AE.

Depressed level of consciousness should not be attributable to another cause (eg, sedating medication).

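### Appendix 14's ICANS management table lists stupor under grade 3 (hold) as well as grade 4 (permanently discontinue); the grade 3 entry is wrong and should be deleted

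*Combined protocol and SAP*

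**What the plan says.** The ICANS management table in Section 10.14 describes each grade and gives the action beside it.

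- **Grade 3.** The descriptors include depressed consciousness "but awakens to tactile stimulus" and, further down the same cell, "Somnolence-obtundation or stupor". The action is "Hold GEN3017 until resolution of ICANS. Management in monitored care or intensive care unit".
- **Grade 4.** The descriptors include a subject who cannot be roused or who "requires vigorous or repetitive tactile stimuli to arouse or stupor or coma". The action is "Permanently discontinue GEN3017. Management in monitored care or intensive care unit".

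The ICANS Assessment and Grading table, later in the same appendix, mentions stupor once, in the grade 4 cell of the consciousness domain: "Patient is unarousable or requires vigorous or repetitive tactile stimuli to arouse. Stupor or coma". Its grade 3 cell covers only subjects who wake to touch.

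Section 8.3.8.1 states that "Overall ICANS grade is determined by the most severe event of the neurotoxicity domains", and the note under the management table repeats this rule.

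For a first grade 3 ICANS event, Table 6-4 (Section 6.7.2.1) says "Withhold GEN3017 until resolution of ICANS event to ≤ grade 1 for at least 72 hours"; it stops treatment permanently only on recurrence. For grade 4 it stops treatment permanently at the first event. Section 6.7.2.2 carries the same guidance into the expansion part as appropriate.

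**The concern.** One clinical sign sits in two adjacent grade rows with opposite drug instructions. The management table is where a site looks to decide what to do with the next dose, and it gives full descriptors for each grade, so a site could read the grade directly from it. Table 6-4 refers the reader to Section 10.14 without naming one of its tables.

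The main stake is the individual subject: GEN3017 could be given again after a first episode of life-threatening neurotoxicity for which the plan intends permanent discontinuation. A secondary stake, in dose escalation, is that the event may not be counted where the safety boundaries expect it.

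**Working it through.** The plan gives no figure on this point to reproduce, so the check is a comparison of text followed by tracing one event through the rules.

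**Step 1. Where stupor appears in Section 10.14**

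| Place | Grade 3 | Grade 4 |
|---|---|---|
| Management table, descriptor | stupor listed | stupor listed |
| Management table, action | hold | permanently discontinue |
| Grading table, consciousness domain | not listed | stupor listed |

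Stupor is placed once at grade 3 and twice at grade 4.

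**Step 2. Which entry is wrong**

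- The grading table has stupor at grade 4 only.
- The arousal criteria in the management table agree with it. A grade 3 subject wakes to touch; a grade 4 subject cannot be roused or needs vigorous or repeated stimulation. Stupor is grouped with the latter.
- Under the most-severe-domain rule, a sign that satisfies a grade 4 domain makes the event grade 4, whatever else is present.
- Both tables cite the same ASTCT consensus source, so they should not differ.

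All four point to grade 4. Only the word stupor conflicts; nothing in the grading table contradicts the rest of that grade 3 descriptor.

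**Step 3. One stuporous event recorded as grade 3**

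- *Dosing.* Table 6-4 lets a first event resume once it has been at grade 1 or lower for 72 hours. Recorded as grade 4, it would lead to permanent discontinuation.
- *Table 6-5.* The boundary in the grade 4 or greater row is 2 events at 2 to 6 subjects dosed and 3 events at 9 and 12. One event recorded a grade too low turns 2 into 1, or 3 into 2. The grade 3 or greater row carries a footnote restricting it to events not resolved to grade 2 or lower within 48 hours. A stuporous event recorded as grade 3 that resolves within 48 hours is therefore counted in neither row. If it does not resolve in that time, it still counts in the grade 3 or greater row.
- *DLT (Section 6.7.1).* The specific bullets make grade 4 ICANS a DLT outright, and grade 3 ICANS a DLT only if unresolved at 48 hours. A general bullet also covers non-hematological toxicity of grade 3 or higher, and its list of exclusions does not name ICANS. If the general bullet applies, the event is a DLT at either grade and nothing changes. If the specific bullets take precedence and the event resolves within 48 hours, one DLT in three subjects becomes none, and Table 4-2 moves from remain to escalate. This effect is conditional on that reading.

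**The case against.** The strongest reply is that the protocol already answers the question. Section 8.3.8.1 says ICANS grading rests on the ICE score and four other neurologic domains, and those five are exactly the rows of the grading table. The most-severe-domain rule is printed directly beneath the management table, so even a reader using that table alone, finding stupor in two rows, is sent to the higher one. To under-grade, a site must overlook that note, the arousal criterion in the same grade 3 cell, the grade 4 row and the grading table.

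There are also safeguards against unreviewed re-dosing. Section 6.7.2.1 requires the medical monitor to approve continued treatment after a DLT, and after a toxicity that would have been a DLT had it fallen inside the evaluation period. ICANS is an adverse event of special interest (Section 8.4.1.1), reportable within 24 hours if serious and 72 hours if not (Section 8.4.3.5).

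Most of this stands, and it makes the likelihood low. It does not defend the grade 3 entry. The safeguards also have a gap: if the specific ICANS bullets govern and the event resolves within 48 hours, a first event recorded as grade 3 is not a DLT, and Table 6-4 states no approval step before resuming. Only the special-interest reporting would then bring it to the sponsor's attention.

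**Conclusion.** The grade 3 entry is wrong as written and should be corrected. It is an internal inconsistency in a table that directs dosing; the likelihood of harm is low, but the consequence for one subject could be serious. The size of the effect cannot be estimated, because the documents give no rate of stupor and no rate of misgrading.

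A reader might infer more than this. The documents do not support the following:

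- **That the grade of stupor is left open.** It is not; the rules in Step 2 settle it at grade 4.
- **That grade 4 always ends treatment.** Table 6-4 and Appendix 14 say so for ICANS, but the general text of Section 6.7.2.1 allows resumption to be considered after a grade 4 non-hematologic DLT, following discussion with the medical monitor.
- **That the effect on Table 6-5 can be sized from its assumed rate.** At the acceptable 5% rate, the chance of at least 2 events in 6 subjects is 1 − 0.95^6 − 6 × 0.05 × 0.95^5 = 3.3%. That is the false-alarm chance for a row pooling CRS and ICANS, not the detection lost through misgrading. At an assumed 20% rate the same formula gives 1 − 0.8^6 − 6 × 0.2 × 0.8^5 = 34.5%. Neither figure measures this problem. Crossing a boundary also leads to a safety review, not an automatic stop.
- **That the CAR-T experience bounds the risk.** Section 2.3.2 reports no ICANS in cHL patients in three trials of 15, 14 and 10 subjects. This supports expecting few events in cHL, but it concerns a different product class and says nothing about misgrading.
- **That the seizure wording in the same grade 3 cell is a second error.** It begins with And where the grading table has Any. In machine-read text this may be an extraction fault, and nothing here rests on it.

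**What to change.** Delete the words *or stupor* from the grade 3 row of the management table in Section 10.14 in the next amendment, and notify sites. Leave the grade 4 row, its other descriptors and its discontinuation instruction as they are.

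Do not go further and declare the grading table the sole basis for dosing. The grade 4 management row also lists life-threatening consequences and the need for mechanical ventilation, which are not stand-alone criteria in the grading table. Such a sentence could move a ventilated subject with no other grade 4 finding from discontinue to hold, and so weaken protection.

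Check the seizure wording against the source PDF before treating it as an error.

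The cost is a two-word deletion and a site notice, with no new procedures or subjects. Section 10.1.5.1 requires a formal amendment with ethics approval and, where locally required, regulatory approval, so the change is best carried with the next one.
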